15.2.3 Reporting Unanticipated Adverse Device Effects

An Investigator shall submit to the sponsor and the reviewing IRB a report of any unanticipated adverse device effect occurring during an investigation as soon as possible, but in no event later than ten (10) working days after the Investigator first learns of the effect (21 CFR 812.150 (a) (1)).

15.2.4 Reporting Deaths

An Investigator shall submit to the sponsor a report of any death occurring during the study as soon as possible without undue delay. All deaths will be reported by the sponsor to the FDA within ten (10) working days of becoming aware of the death.

Send all source documents to the sponsor clinical study team via email.

15.3 Data Safety Monitoring Board (DSMB)

An independent DSMB will be formed to regularly review study progress with regard to safety. At a minimum, the DSMB will meet semi-annually. Members of the DSMB will have no affiliation with the HALO Clinical Study.

A DSMB Manual of Operations will be developed and agreed upon by the sponsor and DSMB members prior to initiation of the trial. The manual will describe the specific functions of the DSMB. The primary responsibilities of the DSMB are to:

- Establish adverse event definitions (and refine definitions as necessary during the conduct of the clinical study)
- The DSMB will act as a Clinical Events Committee (CEC) to adjudicate whether or not adverse events are valve-related and determine the severity of the events
- Review and validate the subject sample (i.e., review inclusion/exclusion deviations and other protocol deviations)
- Provide oversight for issues affecting general subject welfare
- Establish study termination guideline criteria
- Recommend premature study termination

At any time during the course of the study, the DSMB may offer opinions or make formal recommendations concerning aspects of the study that impact subject safety (e.g., safety-related protocol changes or input regarding adverse event rates associated with the investigational study). Additionally, the DSMB may act as an advisory panel for questions regarding informed consent, subject enrollment, protocol implementation, study endpoints, data discrepancies, and other issues that may present during the course of the study.

The DSMB will review all adverse events reported by the site and determine the following: adverse event type, relatedness to the procedure or device (if known), and whether the event is anticipated or unanticipated. Following each DSMB meeting a report will be sent to Investigators indicating the final adjudication of all adverse events reviewed during the meeting.

In all reports to the FDA adverse events will be pulled from the DSMB adjudication unless the adverse event has not been adjudicated, as noted in the report.

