5 ENDPOINTS

5.1 Primary Safety Endpoint

The primary safety endpoint for this study is the actuarial (Kaplan-Meier) rate of total valve-related adverse events experienced through 365 days post implant or until the valve is removed/replaced due to anatomical growth of the subject, whichever occurs first. Valve-related adverse events to be evaluated are:

- Death
- Endocarditis
- Hemorrhage (whether or not due to anticoagulant/antiplatelet medication) [all and serious]
- Nonstructural dysfunction (including perivalvular leak [all and serious], hemolysis, and hemolytic anemia)
- Reoperation (including valve explant, not due to anatomical growth of the subject) [all and valve-related]
- Structural valve deterioration
- Thromboembolism
- Valvular thrombosis

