11 ECHOCARDIOGRAPHY PROCEDURES

Hemodynamic function will be evaluated by calculating the number of observations, mean, standard deviation, minimum and maximum values for each of the following variables:

- Mean pressure gradients across the mitral valve
- Peak pressure gradients across the mitral valve
- Cardiac output
- Cardiac index
- Valvular regurgitation

Transthoracic echocardiogram (TTE) examinations are required for each subject at baseline, post-procedure, 30 days, 6 months, 12 months, and annually thereafter for as long as the valve remains implanted.

The study specifies TTE rather than transesophageal echocardiography (TEE) to minimize subject risk. Echocardiographic data collected from TEE warranted for any other medical purpose is allowed.

For Adjunctive EU/CU Subjects, echocardiograms should be collected from subject's medical records, when available, for visits conducted prior to enrollment. Additionally, echocardiograms should be collected even if any echocardiographic assessments occurred outside of a specified visit window as they may be used as supporting source documentation on the subject.

CDs of the echocardiography exams from each required visit will be forwarded to the echocardiography core laboratory (core lab) for interpretation. The primary responsibility of the core lab is to provide consistent interpretation of TTE data across all study sites by completing the TTE Case Report Form (CRF).

The sponsor will use only the measurements from the core lab for analysis. If the core lab determines the echocardiogram is unreadable, the subject may be asked to return for another echocardiogram.

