15.1 Adverse Event Definitions

Adverse Event:

An adverse event (AE) is any undesirable clinical occurrence that is a negative change from baseline.

Unanticipated Adverse Device Effect (UADE):

Any serious adverse effect on health or safety or any life-threatening problem or death caused by, or associated with a device, if that effect, problem, or death was not previously identified in nature, severity, or degree of incidence in the Investigational Plan including a supplementary plan or application); or any other unanticipated serious problem associated with the device that relates to the rights, safety, or welfare of subjects (21 CFR 812.3(s)).

Serious Adverse Event:

Serious adverse events will be defined as those adverse events resulting in the following; death, life-threatening adverse event, inpatient hospitalization or prolongation of existing hospital stay, persistent or significant disability/incapacity or medically significant event.

Non-serious Adverse Event:

Non-serious adverse events will be defined as those events requiring health care professional directed medical intervention but that are not life threatening, and are not likely to have long-term (> 6 months) sequelae, and do not require long term (> 6 months) therapy.

Anticipated Adverse Events:

Complications associated with replacement mechanical heart valves include, but are not limited to:

- hemolysis;
- infections;
- thrombus;
- thromboembolism;
- valve dehiscence;
- unacceptable hemodynamic performance;

- hemorrhagic complications secondary to anticoagulant medication;
- prosthetic failure;
- heart failure;
- damage to other cardiac structures including the cardiac conduction system;
- obstruction or distorting of adjacent cardiac structures; or
- death.

Any of these complications may require reoperation or explantation of the study valve.

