15.2.2 Reporting Valve-Related Adverse Events

Safety surveillance within this trial (and the safety reporting performed by the investigator) starts:

- as soon as the subject is enrolled for Pivotal IDE subjects enrolled under protocol revision A or B.
- as soon as the subject is enrolled for Adjunctive Prospective Subjects.
- from the time of attempted initial implant (defined as the device physically contacting the subject's cardiac anatomy) for enrolled Adjunctive EU/CU Subjects.

Safety surveillance and safety reporting will continue until the last study visit has been performed, or the subject is deceased, or the subject concludes participation in the trial.

Investigators are responsible for promptly reporting, as soon as they become aware, all serious and non-serious valve-related adverse events as specified in Akins et al.²⁵ to the sponsor by

completing the Adverse Event CRF. Serious adverse events should be reported as specified in Section 15.2.1. Reportable events include:

- Death
- Endocarditis
- Hemorrhage (whether or not due to anticoagulant/antiplatelet medication)
- Nonstructural dysfunction (including perivalvular leak, hemolysis, and hemolytic anemia)
- Reoperation (including valve explant, not due to anatomical growth of the subject)
- Structural valve deterioration
- Thromboembolism (valve-related)
- Valvular thrombosis
- Unanticipated Adverse Device Effects (UADEs)

Refer to Appendix 11 for definitions of all reportable valve-related adverse events. All unresolved adverse events should be followed by the Investigator until resolution. Updates to adverse events should be provided to the sponsor by completing the AE Follow-Up CRF.

The sponsor may request that additional information such as operative notes, clinic notes, discharge summaries, histopathology reports, or a physician's summary of the event be provided to the sponsor as supporting documentation for all reported events.

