Examples of nonstructural dysfunction include: entrapment by pannus, tissue, or suture; paravalvular leak; inappropriate sizing or positioning; residual leak or obstruction after valve implantation or repair; and clinically significant intravascular hemolytic anemia. More than mild recurrent or residual mitral regurgitation after surgical or percutaneous interventional valve procedures (coronary sinus interventions, direct reparative methods, or other methods aimed at achieving ventricular remodeling) is nonstructural dysfunction, unless there is disruption of the valve components themselves, which would then be structural deterioration.

Sudden or progressive dysfunction or deterioration of the study valve may be structural, nonstructural, or both as determined by reoperation, autopsy, or clinical investigation.

Reoperation

Reoperation is any operation that repairs, alters or replaces the study valve. The reasons for reoperation are to be reported and may include reasons other than valve-related morbidity, such as recall, excessive noise, or incidental or prophylactic removal.

Thrombolytic or catheter-aided therapy of valve-related morbidity is not considered reoperation; however, the morbid event that prompted the intervention should be reported.

Structural Valve Deterioration

Dysfunction or deterioration involving the study valve (exclusive of infection or thrombosis), as determined by reoperation, autopsy, or clinical investigation will be reported. Structural valve deterioration refers to changes intrinsic to the valve, such as wear, fracture, poppet escape, calcification, leaflet tear, stent creep, and suture line disruption of components (e.g., leaflets) of the study valve.

Thromboembolism

Any thromboembolic event that occurs in the absence of infection after the immediate perioperative period (when anesthesia-induced unconsciousness is completely reversed) will be reported as valve-related. Thromboembolic events occurring during the procedure will be reviewed and adjudicated by the DSMB to determine if the event is valve or procedure related. Subsets of thromboembolic events are:

Neurologic:

A neurologic thromboembolism is one that results in a central, new neurological deficit, whether temporary or permanent and whether focal or global, that occurs after the subject emerges from anesthesia. Types of neurologic events are:

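### The plan states no step that reconciles core-lab leak findings with site adverse event reports, and its definitions of a reportable leak conflict, so the primary safety rate may miss leaks

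*Combined protocol and SAP*

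**What the plan says.** The primary safety endpoint in section 5.1 is the "actuarial (Kaplan-Meier) rate of total valve-related adverse events experienced through 365 days post implant", or until removal for growth if that is earlier. One component is "Nonstructural dysfunction (including perivalvular leak [all and serious], hemolysis, and hemolytic anemia". All leaks are meant to count, with serious ones also shown separately.

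Events enter through the site. Section 15.2.2 makes investigators responsible for reporting serious and non-serious valve-related events on the adverse event form, and points them to Appendix 11 for definitions. Section 15.3 then says: "The DSMB will review all adverse events reported by the site and determine the following: adverse event type". Reports to the FDA take events from that adjudication.

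Echo data follow a separate path. Under section 11, examinations from required visits go to the core lab, which completes the echo form: "The sponsor will use only the measurements from the core lab for analysis". Section 6.1 has regurgitation, with its site where appropriate, evaluated at each visit. Section 5.2 makes regurgitation a primary effectiveness endpoint.

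Section 15.1 sets the general definitions: "An adverse event (AE) is any undesirable clinical occurrence that is a negative change from baseline", and "Non-serious adverse events will be defined as those events requiring health care professional directed medical intervention". Appendix 11, under Nonstructural Dysfunction, attaches no condition about treatment or the pre-operative state. Its examples include paravalvular leak and "residual leak or obstruction after valve implantation or repair".

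**The concern.** The same echo can inform two primary endpoints through two assessors. For effectiveness, the core lab's reading is used. For safety, the leak must be recognised and filed by a site in an unblinded single-arm study (section 3). If a site does not file it, no stated step brings the core lab's finding to the board that decides what counts.

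Site capture has weak points of its own. Section 9.7 lets the child's primary cardiologist perform follow-up visits, with data passed on to the investigator. For Adjunctive EU/CU subjects, information from before enrolment comes from medical records where available.

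The general definitions add a second difficulty: a site that follows section 15.1 literally can leave out a leak that section 5.1 means to count. A true leak left out can lower the safety rate but never raise it. The study is intended to support a PMA supplement (section 4.1), so an error in that direction matters. The regurgitation table and the safety table could also disagree for the same children without anyone being asked to explain why.

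**Working it through.** The text gives no leak rate, sample size or performance goal for this endpoint, so there is no figure to reproduce. The check compares the sections and then illustrates the size on assumed values.

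**1. Routes into the safety rate.** Section 15.2.2 (site files the event), then section 15.3 (DSMB adjudicates site-reported events), then the reported rate. No other route is described. The opening paragraph on safety, just before section 15.1, says all valve-related events will be collected and adjudicated. That states an aim; sections 15.2.2 and 15.3 supply the mechanism.

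**2. Path of the core-lab reading.** Section 11 ends with the sponsor's analysis. No section sends a leak finding to the DSMB or back to the site, or compares it with filed events. No section forbids this either.

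**3. How each kind of leak is classified.**

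| Leak | Section 15.1 | Section 5.1 and Appendix 11 |
|---|---|---|
| Meets a serious criterion | Serious | Counts |
| Not serious; needs intervention, no therapy or likely sequelae beyond 6 months | Non-serious | Counts |
| Not serious; only observed | Neither class | Counts |
| Residual; milder than the regurgitation before surgery | Ambiguous | Counts (named example) |

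The third row is a direct conflict, because section 15.2.2 asks for serious and non-serious events and this leak is neither. The fourth row is ambiguous because section 9.3 places baseline before the procedure. A leak around a new valve can be read as a new finding, or as no worse than the child's earlier regurgitation.

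**4. Illustration of size.** All inputs are assumed. Let q be the one-year risk from all other components, L the true leak risk and s the share of leaks filed. Take leak as independent of the other components.

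- Rate as reported: R = 1 − (1 − q)(1 − L·s)
- Shortfall against full filing: D = (1 − q)·L·(1 − s)
- q = 20%, L = 10%: full filing gives 1 − 0.8 × 0.9 = 28%; half filed gives 1 − 0.8 × 0.95 = 24%; D = 4 points.
- q = 40%, L = 10%: full filing gives 1 − 0.6 × 0.9 = 46%; half filed gives 1 − 0.6 × 0.95 = 43%; D = 3 points.
- Over q = 20–60%, L = 5–20%, s = 25–75%: smallest D = 0.4 × 0.05 × 0.25 = 0.5 points; largest D = 0.8 × 0.20 × 0.75 = 12 points.
- s = 100%: D = 0.

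Without independence, D is the probability of an unfiled leak in a child with no other event. It lies between 0 and L·(1 − s), provided that product does not exceed 1 − q. With L = 10% and s = 50%, that is 0 to 5 points.

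**The case against.** The strongest reply is that the event-specific rules already cover these leaks. Section 15.2.2 lists perivalvular leak as reportable and refers sites to Appendix 11, which names residual leak and binds the DSMB. A reader might infer from the baseline wording in section 15.1 that residual leaks are excluded. The documents do not support that: the wording is ambiguous, and the specific definition includes them.

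A reader might also infer that core-lab findings never reach the DSMB. That goes too far. The protocol is silent, the DSMB Manual of Operations is not among the documents, and section 15.3 lets the board advise on data discrepancies. Nor is filing optional: section 15.2.2 makes reporting a duty, and section 17.1.3 has monitors review patient records.

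On classification, the serious definition includes medically significant events, so some observed leaks could qualify, and the DSMB determines severity. On size, leak, hemolysis and reoperation may occur in the same child, who is then counted anyway; such overlap would shrink the shortfall. Core-lab coverage is also incomplete: older echoes for EU/CU subjects are collected only if available, and some may be unreadable.

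These points limit the claim but leave two things standing. The protocol states no reconciliation, and section 15.1 conflicts with section 5.1 and Appendix 11 for leaks that are only observed. The DSMB's use of Appendix 11 does not help with an event it is never sent.

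**Conclusion.** The point holds as a gap in ascertainment and a conflict of definitions. Following the stated rules literally can drop untreated leaks from a primary component meant to include all of them, and no stated cross-check would recover them. The leak component, and so the primary safety rate, may be undercounted in the device's favour.

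It would be wrong to conclude that the rate is undercounted by a known amount. The range of 0.5 to 12 points rests wholly on assumed event risks, an assumed filing share and independence. Leaks read by the core lab would still show in the regurgitation results, so the gap concerns the safety rate. The change is worth making because it uses a form and a board that already exist.

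**What to change.** 1. **Section 15.3.** Have the sponsor list to the DSMB every paravalvular leak, and every more-than-mild regurgitation of the study valve, that the core lab records at any post-implant echo. The DSMB adjudicates each under Appendix 11 whether or not the site filed an event. Apply this to the existing core-lab forms of all subjects already enrolled, so that ascertainment is uniform across protocol revisions. Give the echo date in the listing, because the endpoint stops at 365 days while the 12-month visit window of ± 60 days extends past that.
2. **Section 15.1.** State that Appendix 11 prevails for valve-related events whatever the pre-operative baseline, and define non-serious as any adverse event that does not meet the serious definition.

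The echo form is not in the documents. Section 6.1 suggests that it records the site of regurgitation; if it does not, the more-than-mild criterion is the part of the listing that can be applied directly.

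No new visit, test or reader is needed. The cost is a sponsor listing, including a look back over completed forms, and somewhat more adjudication. Because the change bears on how a primary endpoint is ascertained, it may need FDA and IRB approval under section 17.1.2. The resulting safety rate may be less favourable.

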16 CONFIDENTIALITY

All subject information collected during the course of this study will be kept confidential according to applicable state and federal laws and regulations.

The FDA or other US government agencies (including regulatory agencies) and regulatory authorities in other countries may inspect and copy subject records or other information about subjects related to this study.

Any information about subjects that leaves the institution conducting the study will be modified to remove certain information that could identify the subject (e.g., subject's name, age on the day of enrollment, address, and hospital number) and only be identifiable by a subject ID code.

Study data provided to the sponsor that is published in medical journals and/or presented at scientific conferences will not allow the identification of study subjects.

Study results from this study may also be published in scientific journals or presented at conferences as an oral or poster presentation; however, the identity of a study subject will not be disclosed.

17 STUDY ADMINISTRATION

17.1 Study Sponsor

17.1.1 Clinical Project Team

A sponsor clinical project team will be developed and trained to select qualified Investigators, train investigative sites, monitor the clinical study, ensure IRB approval and renewal are obtained, and inform the IRB and FDA of any significant new information about the clinical study. The team will adhere to Abbott/ St. Jude Medical Corporation internal procedures, CFR parts 11, 54, 56, 812 and all other applicable regulations. The Sponsor will avoid improper influence on, or inducement of, the subject, monitor, any Investigators, or other parties participating in or contributing to the clinical study.

17.1.2 Amendments to the Investigational Plan

Investigational Plan amendments may occur during the course of the study and will be reviewed prior to implementation to determine if the changes affect the: validity of the data; risk-to-benefit ratio; scientific soundness of the Investigational Plan; or the rights, safety, or welfare of the human subjects involved in the clinical study.

Investigational Plan amendments that affect any of the above criteria will require FDA and IRB/EC approval prior to implementation. Amendments that do not meet the criteria above will be reported to the FDA according to 21 CFR 812.35.

17.1.3 Monitoring Procedures

Monitoring is necessary to ensure adequate protection of the rights and safety of human subjects and the quality and integrity of the data obtained during the study. It is the responsibility of the sponsor of the study to ensure proper monitoring of the investigation and to see that all the clinical requirements are met. Monitoring activities will be conducted according to the Investigational Plan, Clinical Trial Agreement, ICH GCP guidelines, 21 CFR 812, and FDA guidance relevant to this clinical study.

A monitor will visit the investigator or designee periodically during the study to monitor progress, to assist in gathering the required data and to answer any questions. During

these visits, the clinical monitor will review the patient's records to verify that all records and files are up to date and assure compliance with all requirements of the protocol and FDA regulations.

The investigator will make patient and study records available to the clinical monitor for periodic inspection.

